	
administration of 200 µg/ 5 mCi Tc 99m tilmanocept approximately one week apart. At least one subject enrolled into each cohort must meet inclusion criteria 4c, as defined above (suspected non-cutaneous or confirmed non-cutaneous KS). For determination of the primary endpoint, a review meeting for safety will be held after the completion of each cohort prior to opening the next dose cohort. Cohorts will be dosed per the following table:
 

	Tc 99m tilmanocept Dose	Route of Administration	Number of Subjects	

Cohort 1	100 µg/ 5 mCi	IV	n = 4	

Cohort 2	100 µg/ 10 mCi	IV	n = 4	

Cohort 3	200 µg/ 5 mCi	IV and SC	n = up to 6	

 
Following IV administration, all subjects will have a whole body planar scan with optional SPECT/CT region of interest scanning beginning at 60-75 minutes post-injection. Subjects in Cohort 3 will additionally have a whole body planar scan with optional SPECT/CT region of interest scanning beginning at 60-75 minutes and 4-6 hours following SC injection.
		Tc 99m tilmanocept Dose	Route of Administration	Number of Subjects	Cohort 1	100 µg/ 5 mCi	IV	n = 4	Cohort 2	100 µg/ 10 mCi	IV	n = 4	Cohort 3	200 µg/ 5 mCi	IV and SC	n = up to 6
	Tc 99m tilmanocept Dose	Route of Administration	Number of Subjects														
Cohort 1	100 µg/ 5 mCi	IV	n = 4														
Cohort 2	100 µg/ 10 mCi	IV	n = 4														
Cohort 3	200 µg/ 5 mCi	IV and SC	n = up to 6														

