1.2.1 Prior Experience of Tilmanocept Injection in KS Patients

Imaging of KS with high specificity and sensitivity has been a remarkable challenge even with today's high resolution technology and available imaging agents⁽¹⁷⁻²⁹⁾. In addition to the ex vivo study, [name] completed a phase II clinical pilot study in KS patients at the University of California San Francisco (UCSF Protocol 14-13522). Five subjects received a subcutaneous injection of 50 µg tilmanocept radiolabeled with 2.0 mCi Tc 99m. No subjects experienced any SAEs. Three AEs were reported in two subjects, including peripheral edema (probably not related to study drug or procedures) and fatigue and nausea (possibly related to study drug or procedures). No interaction of tilmanocept with HAART therapy or other drugs utilized in the treatment of HIV or HHV8 was observed.

Tc 99m tilmanocept localized regionally in clinically confirmed KS lesions as well as lymph nodes, as shown in [Figure 4](#). Thus, this receptor targeting approach to CD206 presents itself as a novel portal for imaging and staging KS. Based on this previous experience, it is anticipated that IV-administered Tc 99m tilmanocept will be able to systemically localize both cutaneous and non-cutaneous (i.e. visceral or CNS) KS lesions.

Figure 4. Localization of Tc 99m Tilmanocept in KS Lesions

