1.3.1 Nonclinical Evaluations – IV and Intraperitoneal Administration

Nonclinical studies with tilmanocept demonstrated that the drug selectively binds to its intended receptor (the MBR), is appropriately distributed for radio detection of lymphatic tissue, and is well tolerated by rats, rabbits, guinea pigs, and dogs.

PK (pharmacokinetics) data obtained from SC repeated dose toxicity studies in rats and dogs demonstrated that absorption into the plasma was rapid in both species. Urinary excretion was a major pathway of elimination. A tissue distribution study demonstrated that tilmanocept exhibited rapid clearance from the injection site, rapid uptake by the local lymph node, and low uptake by the remaining lymph nodes. In addition, substantial accumulation was noted in the kidneys, bladder, and bladder contents by 3 hours post dose, providing additional evidence that urinary excretion occurs rapidly and is a major route of elimination. Tilmanocept was well tolerated at all doses tested in nonclinical safety pharmacology studies and in a number of single and repeated dose toxicology studies in rats, rabbits, and dogs. In some studies in rabbits and dogs, tilmanocept acted as a local irritant of the subcutis or skeletal muscle, and induced mild inflammation and tissue degeneration. The no-observed adverse-effect level (NOAEL) in the definitive repeated dose studies in rats and dogs was 42 μ g/kg/day.

Tilmanocept was not mutagenic or genotoxic in vitro (mouse lymphoma test, Ames test) or in vivo (mouse micronucleus test). No signs or symptoms of hypersensitivity were observed in an in vivo study

in male guinea pigs. Most of the nonclinical safety studies used SC drug administration, a proposed route for administration to humans. The human dose for clinical studies is 50 µg Tilmanocept per procedure, equivalent to 0.714 µg/kg if a conservative estimate of 70 kg is used for human body weight. The single dose administration in animals ranged from 14 to 280 µg/kg in animals, which is approximately 20 to 390 times the human µg/kg dose. Repeated doses in animals ranged from 10.5 to 42 µg/kg/day in animals and are approximately 15 and 60 times the human µg/kg dose. These doses were all well tolerated in the nonclinical studies.

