
Under these experimental conditions, there was little or no evidence of direct, time- or metabolism-dependent inhibition of any CYP enzyme by tilmanocept.

ABC and SLC transporters: It was found that tilmanocept was not an inhibitor of human transporters (namely P-gp, BRCP, OAT1B1, OATP1B3, OAT1, OAT3, and OCT2) under the conditions tested.

Hemolysis: No hemolysis and no flocculation were observed following in vitro treatment of human whole blood with tilmanocept at final whole blood concentrations of 2.5, 25 or 250 µg/mL.

Ion Channels (Na⁺, K⁺, Ca²⁺): Although there is a small dose-dependent effect that is fractional to the positive control, variability within concentration renders the median value observations not significantly different (Kruskal-Wallis).

1.3.2 Clinical Pharmacokinetics and Pharmacodynamics in Lymphatic Mapping Clinical Trials (Subcutaneous, Peritumoral and Intradermal administration)

After a single peritumoral (PT), ID, or SC dose for solid tumor lymphatic mapping, Tc 99m tilmanocept demonstrated significantly faster injection site clearance than Tc 99m sulfur colloid (TcSC, filtered and unfiltered), the standard imaging agent and comparator used in the Phase 1 trials.

The mean Tc 99m tilmanocept injection site clearance half-life was approximately 2 to 3 hours vs. approximately 15 to 27 hours for TcSC. Absolute uptake in the primary “sentinel” lymph node (L_{SN}) was dose-related for Tilmanocept, although relative nodal uptake (%ID_{SN}) overall was independent of dose and ranged from 0.05%ID_{SN} to 1.81%ID_{SN}, while the TcSC values ranged from 0.64%ID_{SN} to 3.66%ID_{SN}; differences between Tc 99m tilmanocept and TcSC were not statistically significant.

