5.2 Investigational Product Dosage and Administration

This study includes IV administration of 3 doses Tc 99m tilmanocept: 100 μ g/ 5 mCi, 100 μ g/ 10 mCi, and 200 μ g/ 5 mCi. All subjects will receive IV administration at one of these three doses. Cohort 3 will serve as a comparator arm, and Cohort 3 subjects will additionally receive a SC injection of Tc 99m tilmanocept at the Cohort 3 dose of 200 μ g/ 5 mCi (see Table 1). At least one subject enrolled into each cohort must meet inclusion criteria 4c (suspected non-cutaneous or confirmed non-cutaneous KS), as described in [Section 4.1](#).

Table 1. Dosing Cohorts

	Tc 99m tilmanocept Dose	Route of Administration	Number of Subjects
Cohort 1	100 μ g/ 5 mCi	IV	n = 4
Cohort 2	100 μ g/ 10 mCi	IV	n = 4
Cohort 3	200 μ g/ 5 mCi	IV and SC	n = up to 6

All subjects will receive Tc 99m tilmanocept through an IV route of administration. A single syringe will be used and injected as a slow push into the venous catheter. The preferred site of catheter placement will be the left or right antecubital vein. Injection volume will be 1.0 mL in sterile normal saline. At the completion of the injection, a 10 cc sterile normal saline flush will be administered.

Cohort 3 subjects will also receive Tc 99m tilmanocept through a SC route of administration. Two syringes will be used and injected bilaterally as a slow push into the ankle(s) or the dorsal surface of the foot (feet). Total injection volume will be 1.0 mL (0.5 in each syringe) in sterile normal saline. Each syringe will contain half of the intended total dose of 200 μ g/ 5 mCi (100 μ g/ 2.5 mCi per syringe).

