If < 50 lesions overall, enter code 11 ("total body") as the representative area.

Definition of a flat lesion: Area of skin that is hyperpigmented but not raised (i.e., the borders are not palpable; e.g., macule or patch are examples of flat lesions).

Definition of a raised lesion: any lesion that protrudes from skin surface and is palpable (e.g., plaque, nodule, or tumor)

3. Representative site
(Site Code) Number of FLAT lesions
(macule/patch) Number of RAISED lesions
(plaque/nodule/tumor)

I.

II.

[figure not shown]
III.

Questions 4-6 relate to lesions anywhere on the body:

[figure not shown]
Identify the KS-suspicious lesion with the **largest diameter** in its footprint on the skin.

This can be a flat or raised lesion.

4. Record, in mm, this diameter as well as the diameter that is perpendicular to the largest diameter (as in the image shown).

5. How many KS-suspicious lesions are present which meet the definition a tumor? A tumor is substantially raised above the surface of the skin, the height is nearly the same or greater than the footprint on the skin, and at least one diameter on the footprint of the skin is at least 20 mm (2 cm).

6. What is the vertical height (in mm, as in image shown) of the tallest KS-suspicious lesion?

mm

B. Feet

7. Are there KS-suspicious lesions present on either foot (below a horizontal transection at the ankle)?

Yes

No → **Skip to 9**

Right Left

8. How many flat or raised lesions are on each foot?

Flat

Raised (plaque/nodular/tumor)

C. Oral Cavity

9. Are there any KS-suspicious lesions in the oral cavity? Yes

No → **Skip to 11**

10. Evaluation of oral cavity by site.

Oral Site	KS Lesions		Mark all that apply	
	Absent	Present	Raised	Flat
Gingiva/gums				
Hard palate				
Soft palate				
Buccal mucosa				
Tongue				
Floor of mouth				
Tonsils				

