4.2 Analysis of Efficacy Variables

Localization in KS Sites

The number and percentage of subjects with at least one biopsy-confirmed or clinically suspected KS lesion that has localized with Tc 99m tilmanocept by planar and/or SPECT/CT imaging will be computed. A 95% exact confidence interval on the per-subject localization rate will be computed. This analysis will be performed by dose group and route of administration.

Per-lesion/region localization of Tc 99m tilmanocept by planar and/or SPECT/CT imaging will be computed across all biopsy-confirmed or clinically suspected KS lesions of all subjects. A 95% exact confidence interval on the per-lesion/region localization will be calculated. This analysis will be performed by dose group and route of administration.

An analysis table will also be provided to display the counts of KS lesions localized by imaging that were not previously identified clinically.

Concordance between IV and SC tilmanocept in biopsy-confirmed or clinically-suspected KS lesion sites will be assessed with a cross-tabulation of the IV and SC findings, including the joint probability distribution. The sampling unit for this analysis will be the site. An exact conditional version of McNemar's test will be performed to test the hypotheses

$$H_0: \pi_{IV} = \pi_{SC}$$
$$H_A: \pi_{IV} \neq \pi_{SC},$$

where π_{IV} and π_{SC} represent the probabilities of localization with IV (only) tilmanocept and SC (only) tilmanocept, respectively. In addition, the number and proportion of subjects with concordance and reverse concordance of observed sites of discrete localization of Tc 99m tilmanocept following IV and SC localization will be summarized.

Localization Intensity by Planar and/or SPECT/CT Imaging

Tc 99m tilmanocept average pixel intensity and percent above background will be summarized with descriptive statistics (mean, standard deviation, minimum, median, maximum, and range) for each biopsied lesion localized on imaging following IV injection of Tc 99m tilmanocept by dose group. Summary statistics will be presented separately by imaging type (planar, SPECT/CT).

Proportion of CD206-expressing Cells

Per biopsied-lesion proportion of CD206-expressing cells as determined by histology and IHC fluorescence will be summarized by descriptive statistics (mean, standard deviation, minimum, median, maximum, and range) by dose group.

Localization in Non-KS Sites

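### KS lesions in the SC injection field count in the Cohort 3 IV-versus-SC table, with no rule for sites where the injection depot can drive the SC read

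*SAP*

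**What the plan says.** - **Injection.** Protocol 5.2, for Cohort 3 SC dosing: "Two syringes will be used and injected bilaterally as a slow push into the ankle(s) or the dorsal surface of the foot (feet". It adds: "Each syringe will contain half of the intended total dose of" 200 µg/5 mCi, so each side receives 2.5 mCi.
- **Scans.** The Protocol synopsis (Study design) gives Cohort 3 a "whole body planar scan with optional SPECT/CT region of interest scanning beginning at 60-75 minutes and 4-6 hours following SC injection".
- **Clearance.** Protocol 1.3.2, from the lymphatic mapping trials: "The mean Tc 99m tilmanocept injection site clearance half-life was approximately 2 to 3 hours".
- **Lesion sites.** Protocol Appendix 5 lists the feet as site codes 23 and 24 and the legs as 19 and 20. Its section B asks "Are there KS-suspicious lesions present on either foot (below a horizontal transection at the ankle" and then counts flat and raised lesions on each foot.
- **Definition of localized.** SAP 1.1.1 makes this a visual judgement of illumination against background. SAP 4.1 records it as positive or negative for each anatomic site.
- **Route comparison.** SAP 4.2: "Concordance between IV and SC tilmanocept in biopsy-confirmed or clinically-suspected KS lesion sites will be assessed with a cross-tabulation". The site is the sampling unit and the test is an exact conditional McNemar test. The Table 9 shell in SAP Appendix B has only localized and not-localized categories for each route. Tables 5, 6 and 8 carry separate Cohort 3 IV and Cohort 3 SC rows.
- **Data already captured.** Listing 15 holds the anatomic location of each injection; Listing 20 holds the location of each lesion.

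Neither document says how to read or tabulate a KS site that lies at the SC injection site.

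**The concern.** Agreement between the IV and SC routes is a stated secondary objective (Protocol 2.2). At a lesion away from the needle, a positive SC read means that tracer left the injection site and accumulated in the lesion. At a lesion under or beside the needle, there is strong activity whatever the lesion does. The physician may then call the site illuminated, or may be unable to see the lesion and call it not localized. In both cases the entry in Table 9 can depend on where the needle went.

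Only Cohort 3 supplies pairs, and it has at most six subjects, so a handful of such sites can move the table. At subject level, one lesion read as positive inside the depot makes that subject localized in the Cohort 3 SC row of Table 5. With no rule written in advance, the handling would be settled once the images are in view.

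**Working it through.** **1. The plan's own figure.** 4 + 4 + 6 = 14, which reproduces the stated maximum enrolment. No number of sites, power or significance level is given for the route comparison; 0.05 is assumed below. If each foot code is one site, Cohort 3 can contribute at most 6 × 2 = 12 foot sites.

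**2. Activity left at the injection sites.** Fraction left = 0.5^(t/h), with half-life h = 2 or 3 h (Protocol 1.3.2) and t from the scan windows. The per-side figure is half.

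| Time after SC injection | h = 2 h | h = 3 h | Per side |
|---|---|---|---|
| 1 h | 70.7% | 79.4% | 35.4-39.7% |
| 1.25 h | 64.8% | 74.9% | 32.4-37.5% |
| 4 h | 25.0% | 39.7% | 12.5-19.8% |
| 6 h | 12.5% | 25.0% | 6.2-12.5% |

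The range is 65-79% at 60-75 minutes and 12.5-40% at 4-6 hours. The documents do not say which of the two SC scans feeds Table 9, so both matter.

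**3. Scale.** The highest sentinel-node uptake in Protocol 1.3.2 is 1.81% of the dose. Each side's depot is 32.4/1.81 = 17.9 to 39.7/1.81 = 21.9 times that on the first scan, and 3.5 to 11.0 times on the second. Physical decay affects both alike and cancels. This is a yardstick only, since no KS lesion uptake is reported.

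**4. Effect on the test.** With d discordant sites, all SC-only, the two-sided exact p-value is 2 × 0.5^d.
- d = 5 gives 0.0625; d = 6 gives 0.031. Three subjects with lesions on both feet, read as positive on SC and unseen on IV, would be enough.
- With 3 IV-only and 3 SC-only sites elsewhere, p = 1.0. Nine added SC-only sites (3 against 12) give p = 0.035; eight (3 against 11) give 0.057.

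**5. Chance of p ≤ 0.05 when the routes are truly equal.** Assumptions: 24 sites outside the field; all sites and both routes independent; true localization rate p by each route; every field site forced the same way on SC. Outside the field, IV-only and SC-only each have probability p(1 − p). A field site forced positive is SC-only with probability 1 − p; one forced negative is IV-only with probability p.

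| p | Forced read | Field sites excluded | 4 kept | 8 kept | 12 kept |
|---|---|---|---|---|---|
| 0.5 | either way | 0.024 | 0.043 | 0.104 | 0.206 |
| 0.3 | SC positive | 0.023 | 0.059 | 0.194 | 0.413 |
| 0.7 | SC positive | 0.023 | 0.030 | 0.054 | 0.096 |

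If SC is forced negative, the 0.3 and 0.7 rows change places.

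**6. Effect on the rates (illustrative assumptions only).** Suppose both routes truly detect 60% of sites and a share f = 0.2 to 0.4 lies in the field. All read positive: 0.6 + 0.4f = 68% to 76%, a spurious +8 to +16 points for SC. All masked: 0.6 − 0.6f = 48% to 36%, a spurious −12 to −24 points. Neither the 60% nor the share comes from the documents.

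**The case against.** The read is a specialist's judgement, and a nuclear medicine physician will usually recognise an injection depot. Protocol 7.9 requires a technical-adequacy check, SPECT/CT is available, and SAP 4.2 speaks of discrete localization in its additional summary. Each injection is 0.5 mL, so a plantar or toe lesion may lie clear of it. The comparison is secondary, in a Phase 1 safety study whose SAP 2.1 calls all results descriptive. Listings 15 and 20 would allow a later sensitivity analysis.

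Part of this stands. It limits the stakes, and it rules out treating every foot lesion as compromised. It does not supply the missing rule: the adequacy check concerns the scan as a whole, SPECT/CT is optional, discrete localization is undefined and is not applied to the McNemar table, and a reader who recognises the depot has no category in Table 9 to put it in.

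Four stronger readings are tempting, and the documents do not support them.
- A reader might infer that the depot determines the result at every foot and ankle site, or that it favours SC. The extent of the field and the direction of the error are not given.
- A reader might infer from "tilmanocept acted as a local irritant of the subcutis or skeletal muscle, and induced mild inflammation" (Protocol 1.3.1) that the SC injection also distorts the IV scan about a week later. That sentence concerns some studies in rabbits and dogs; nothing in the documents shows such an effect on a human IV scan.
- A reader might take "Tc 99m tilmanocept localized regionally in clinically confirmed KS lesions as well as lymph nodes" (Protocol 1.2.1) to mean that pooling lesions near and far from the feet is a bias. If SC reaches only regional lesions, that is a real difference between routes, and splitting the table by drainage is a matter of preference.
- A reader might extend the point to Table 7. That table counts lesions not seen clinically, so clinically identified foot lesions cannot be in it.

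**Conclusion.** The point holds in limited form. The plan puts KS sites in the SC injection field into a two-category comparison although, by the protocol's own clearance figure, a large part of the dose is still at those sites on the first scan and an appreciable part on the second. The SC read there can reflect the depot instead of the lesion. That the depot actually changes a given read is an inference, and the half-life is carried over from lymphatic mapping to KS.

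The size cannot be fixed. The effect is confined to Cohort 3 subjects with lesions in the field, and their number is not given. The error probabilities and the point ranges above assume independent sites, all forced one way; a mixture of false-positive and masked reads would partly cancel. The small count of sites needed to reach p ≤ 0.05 is exact arithmetic, given that level. The matter affects a secondary objective and not the primary safety endpoint, but it should be settled before Cohort 3 images are analysed.

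**What to change.** Add a rule to SAP 4.2, with matching notes on the table shells:
- Define the injection field from the recorded injection location (Listing 15) and the lesion location (Listing 20). Include ankle lesions coded under leg sites 19 or 20, and do not simply remove everything coded 23 or 24.
- Treat KS sites in that field as not evaluable for the route comparison, and exclude those pairs from Table 9 for both routes.
- For the Cohort 3 contrast in Tables 5, 6 and 8, show both the IV and the SC rows on the same reduced site set. Removing sites from the SC rows alone would leave adjacent rates that cover different lesions.
- State how many sites are excluded, and identify any subject left with no evaluable site.
- Keep the all-sites version as a sensitivity table.

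This needs SAP wording and table rows only, with no new data and no change to where the dose is given. The cost is fewer IV/SC site pairs from a cohort of at most six subjects.

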9.5.3 Analysis of Efficacy Variables

The number and percentage of subjects with at least one biopsy-confirmed or clinically suspected KS lesion that has localized with Tc 99m tilmanocept by planar and/or SPECT/CT imaging will be

computed. A 95% exact confidence interval on the per subject localization rate will be computed. This analysis will be performed by dose.

Per region lesion localization of Tc 99m tilmanocept by planar and/or SPECT/CT imaging will be computed across all biopsy-confirmed or clinically suspected KS lesions of all subjects. A 95% exact confidence interval on per region lesion localization will be calculated. This analysis will be performed by dose.

Localization intensities of biopsied lesions will be summarized by descriptive statistics (mean, median, standard deviation, minimum, maximum and range) for each dose.

Per biopsied lesion proportion of CD206-expressing cells and quantity of CD206 as determined by histology and IHC fluorescence will be summarized by descriptive statistics (mean, median, standard deviation, minimum, maximum and range) for each dose.

Concordance between between IV and SC tilmanocept in biopsy-confirmed or clinically suspected KS lesion sites will be assessed with a cross-tabulation including the joint probability distribution. The site will be the sampling unit for this analysis. An exact version of McNemar's test will be performed, testing the null hypothesis

$$H_0: \pi_{IV} = \pi_{SC}$$

$$H_A: \pi_{IV} \neq \pi_{SC}$$

where π_{IV} and π_{SC} represent the probabilities of localization with IV (only) tilmanocept and localization with SC tilmanocept only respectively.

In addition, descriptive statistics will be generated relative to the concordance and reverse concordance of observed sites of discrete localization of Tc 99m tilmanocept following IV and SC administration.

The number and percentage of subjects with at least one anatomical site other than KS that has been localized with Tc 99m tilmanocept by SPECT imaging will be computed. A 95% exact confidence interval on the per subject localization rate will be computed. This analysis will be performed by dose and overall.

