2.0 Data Analysis Considerations

2.1 Types of Analyses

All results will be based on descriptive statistics. Unless otherwise stated, continuous variables will be summarized via sample size, mean, standard deviation, median, minimum, and maximum. Categorical variables will be summarized via frequency counts and percentages.

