	Female	xxx (xxx%)	xxx (xxx%)	xxx (xxx%)	xxx (xxx%)
Race	American Indian or Alaska Native	xxx (xxx%)	xxx (xxx%)	xxx (xxx%)	xxx (xxx%)
	Asian	xxx (xxx%)	xxx (xxx%)	xxx (xxx%)	xxx (xxx%)
Race	Black or African American	xxx (xxx%)	xxx (xxx%)	xxx (xxx%)	xxx (xxx%)
	Native Hawaiian or Other Pacific Islander	xxx (xxx%)	xxx (xxx%)	xxx (xxx%)	xxx (xxx%)
Race	White	xxx (xxx%)	xxx (xxx%)	xxx (xxx%)	xxx (xxx%)
	Other	xxx (xxx%)	xxx (xxx%)	xxx (xxx%)	xxx (xxx%)
Ethnicity	Hispanic or Latino	xxx (xxx%)	xxx (xxx%)	xxx (xxx%)	xxx (xxx%)
	Not Hispanic or Latino	xxx (xxx%)	xxx (xxx%)	xxx (xxx%)	xxx (xxx%)

Cohort 1 = 100µg/5mCi IV; Cohort 2 = 100µg/10mCi IV; Cohort 3 = 200µg/5mCi IV and SC.
 STAKING Clinical Services (DD-MMM-YYYY)
 Source Program: xxxxxxxx.sas

Page x of y

Table 4. Summary of Study Drug Administration by Cohort
 Navidea Biopharmaceuticals - Study No. NAV3-24
 Safety Population (N=xxx)

	Group	Mean	Std Dev	n	Min	Max	Median
Tc 99m Dose (mCi)	Cohort 1 IV	xxxx	xxxx	xx	xxxx	xxxx	xxxx
	Cohort 2 IV	xxxx	xxxx	xx	xxxx	xxxx	xxxx
	Cohort 3 IV	xxxx	xxxx	xx	xxxx	xxxx	xxxx
	Cohort 3 SC	xxxx	xxxx	xx	xxxx	xxxx	xxxx
Mass Dose (µg)	Cohort 1 IV	xxxx	xxxx	xx	xxxx	xxxx	xxxx
	Cohort 2 IV	xxxx	xxxx	xx	xxxx	xxxx	xxxx
	Cohort 3 IV	xxxx	xxxx	xx	xxxx	xxxx	xxxx
	Cohort 3 SC	xxxx	xxxx	xx	xxxx	xxxx	xxxx

Cohort 1 = 100µg/5mCi IV; Cohort 2 = 100µg/10mCi IV; Cohort 3 = 200µg/5mCi IV and SC.

STATKING Clinical Services (DD-MMM-YYYY)

Source Program: xxxxxxxx.sas

Table 5. Subject-Level Localization of KS Lesions-Nuclear Medicine Findings
 Navidea Biopharmaceuticals - Study No. NAV3-24
 ITD Population (N=xxx)

Group	Number of Subjects	Number (Proportion) Localized	95% Exact One-Sided Binomial CI for Proportion
Cohort 1 IV	xx	xxx (xxx)	(xxx, xxx)
Cohort 2 IV	xx	xxx (xxx)	(xxx, xxx)
Cohort 3 IV	xx	xxx (xxx)	(xxx, xxx)
Cohort 3 SC	xx	xxx (xxx)	(xxx, xxx)
All Cohorts Combined	xx	xxx (xxx)	(xxx, xxx)

Cohort 1 = 100 μ g/5mCi IV; Cohort 2 = 100 μ g/10mCi IV; Cohort 3 = 200 μ g/5mCi IV and SC.
 STATKING Clinical Services (DD-MMM-YYYY)
 Source Program: xxxxxxxx.sas

Table 6. Lesion-Level Localization of KS Lesions-Nuclear Medicine Findings
 Navidea Biopharmaceuticals - Study No. NAV3-24
 ITD Population (N=xxx)

Group	Number of Clinically Identified Lesions ^a	Number (Proportion) Localized by Imaging	95% Exact One-Sided Binomial CI for Proportion
Cohort 1 IV	xx	xxx (xxx)	(xxx, xxx)
Cohort 2 IV	xx	xxx (xxx)	(xxx, xxx)
Cohort 3 IV	xx	xxx (xxx)	(xxx, xxx)
Cohort 3 SC	xx	xxx (xxx)	(xxx, xxx)

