All Cohorts Combined	xx	xxx (xxx)	(xxx, xxx)

^a Number of cutaneous and non-cutaneous lesions identified in screening.

Cohort 1 = 100 μ g/5mCi IV; Cohort 2 = 100 μ g/10mCi IV; Cohort 3 = 200 μ g/5mCi IV and SC.

STATKING Clinical Services (DD-MMM-YYYY)

Source Program: xxxxxxx.sas

Page x of y

Table 7. Additional KS Lesions Identified from Imaging That Were Not Seen Clinically - Nuclear
Medicine Findings
Navidea Biopharmaceuticals - Study No. NAV3-24
ITD Population (N=xxx)

Group	Number of Identified Lesions	Number (Proportion) of Subjects with at Least 1 Identified Lesion
Cohort 1 IV	xx	xxx (xxx)
Cohort 2 IV	xx	xxx (xxx)
Cohort 3 IV	xx	xxx (xxx)
Cohort 3 SC	xx	xxx (xxx)
All Cohorts Combined	xx	xxx (xxx)

Cohort 1 = 100 μ g/5mCi IV; Cohort 2 = 100 μ g/10mCi IV; Cohort 3 = 200 μ g/5mCi IV and SC.
STATKING Clinical Services (DD-MMM-YYYY)
Source Program: xxxxxxxx.sas

Table 8. Lesion-level Non-Localization of KS Lesions - Nuclear Medicine Findings
 Navidea Biopharmaceuticals - Study No. NAV3-24
 ITD Population (N=xxx)

Group	Number of Clinically Identified Lesions ^a	Number (Proportion) Not Localized by Imaging	95% Exact One-Sided Binomial CI for Proportion
Cohort 1 IV	xx	xxx (xxx)	(xxx, xxx)
Cohort 2 IV	xx	xxx (xxx)	(xxx, xxx)
Cohort 3 IV	xx	xxx (xxx)	(xxx, xxx)
Cohort 3 SC	xx	xxx (xxx)	(xxx, xxx)
All Cohorts Combined	xx	xxx (xxx)	(xxx, xxx)

^a Number of cutaneous and non-cutaneous lesions identified in screening.
 Cohort 1 = 100 μ g/5mCi IV; Cohort 2 = 100 μ g/10mCi IV; Cohort 3 = 200 μ g/5mCi IV and SC.
 STATKING Clinical Services (DD-MMM-YYYY)
 Source Program: xxxxxxxx.sas

Page x of y

Table 9. Number and Percentage of Concordant and Reverse Concordant Lesions
Navidea Biopharmaceuticals - Study No. NAV3-24
ITD Population (N=xxx)

IV Result	SC Result		Total	Concordance	Reverse Concordance	p-Value (McNemar's Test)
	Localized	Not Localized				
Localized	xx (xxx%)	xx (xxx%)	xx (xxx%)	xxx (xxx%)	xxx (xxx%)	xxx
Not Localized	xx (xxx%)	xx (xxx%)	xx (xxx%)			
Total	xx (xxx%)	xx (xxx%)				

STATKING Clinical Services (DD-MMM-YYYY)
Source Program: xxxxxxxx.sas

Page x of y

Table 10. Summary of Imaging-Localized Biopsied Lesion Localization Intensity by Cohort -
 Imaging = Planar
 Navidea Biopharmaceuticals - Study No. NAV3-24
 ITD Population (N=xxxx)

Group	Variable ^a	Mean	Std Dev	n	Min	Max	Median
Cohort 2 IV	Avg Pixel Intensity Percent Above Background	xx xx	xx xx	xx xx	xx xx	xx xx	xx xx

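### The site-level McNemar test and the pooled lesion-level exact intervals treat lesions within a subject as independent, so with 4 to 6 subjects per group they can understate uncertainty.

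*SAP*

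**What the plan says.** For lesion-level localization, SAP 4.2 pools the KS lesions of all subjects and states "A 95% exact confidence interval on the per-lesion/region localization will be calculated", by dose group and route. The shells for Tables 6 and 8 use the number of clinically identified lesions as denominator and head the interval column "95% Exact One-Sided Binomial CI for Proportion".

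For IV versus SC in KS sites, SAP 4.2 plans a cross-tabulation and an exact conditional McNemar test with stated null and alternative hypotheses: "The sampling unit for this analysis will be the site". Protocol 9.5.3 agrees: "The site will be the sampling unit for this analysis". The end of the same SAP paragraph promises "the number and proportion of subjects with concordance and reverse concordance of observed sites", whereas Table 9 is titled "Number and Percentage of Concordant and Reverse Concordant Lesions" and has a p-value column. SAP 2.1 says "All results will be based on descriptive statistics".

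Neither document mentions within-subject correlation, a clustered or stratified test, or a cap on lesions per subject for these analyses.

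**The concern.** A Clopper-Pearson interval and an exact McNemar test both assume that each unit contributes independent information. Lesions in one person share an injection, a scan session, a reader and a biology. If localization is correlated within subject, the pooled interval is too narrow.

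The McNemar test is affected under a narrower condition. Its p-value is too small only if the direction of discordance (IV-only or SC-only) clusters within subject. Subjects who merely differ in overall localization rate do not inflate it. Protocol 1.2.1 gives a possible reason for directional clustering. After SC injection in the earlier KS study, "Tc 99m tilmanocept localized regionally in clinically confirmed KS lesions as well as lymph nodes", whereas IV tracer is anticipated to localize systemically. With SC injection at the ankles or feet, the route that misses a lesion may depend on where a subject's lesions lie. That last step is an inference, not something the protocol states.

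Table 9 carries the only p-value in the table shells and serves a stated secondary objective, so a misleadingly small value there could be read as evidence of a difference between routes.

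**Working it through.** **Inputs from the documents.** Cohorts have 4, 4 and up to 6 subjects (Table 1 of each document); 4 + 4 + 6 = 14 reproduces the total in SAP 1.3. There is no planned precision or power to reproduce. Only Cohort 3 receives both routes, so at most 6 subjects feed Table 9. The lesion form in protocol Appendix 5 has count bands of 1–49 and 50 or more, and 15 cutaneous site codes (12 to 26), so several units per subject are foreseen.

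**Assumptions (not in the documents).** ICC ρ = 0.1, 0.3, 0.5; equal numbers of units per subject; true localization rate 0.7; 10%, 20% or 40% of sites discordant.

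**1. Extremes by hand.**
- One subject with 10 sites discordant in the same direction: p = 2 × (1/2)^10 = 0.002, with no other subject contributing.
- Four subjects with all of 10 lesions localized each: pooled two-sided lower limit 0.025^(1/40) = 0.91. Under complete within-subject dependence there are only 4 independent units: 0.025^(1/4) = 0.40.

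**2. Coverage of the pooled 95% exact interval.** Each subject's count is beta-binomial with mean π = 0.7 and correlation ρ, that is, Beta(π(1−ρ)/ρ, (1−π)(1−ρ)/ρ). Subject counts are convolved exactly, and coverage is the total probability of the outcomes whose interval contains π.

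| Subjects × lesions | Interval | ρ = 0 | 0.1 | 0.3 | 0.5 |
|---|---|---|---|---|---|
| 4 × 5 | two-sided | 97.5% | 94.2% | 86.3% | 78.2% |
| 4 × 10 | two-sided | 96.1% | 86.3% | 70.0% | 59.5% |
| 6 × 10 | two-sided | 96.7% | 87.6% | 72.2% | 62.1% |
| 14 × 10 | two-sided | 95.7% | 85.8% | 70.4% | 60.6% |
| 4 × 5 | one-sided lower | 96.5% | 93.5% | 87.4% | 82.2% |
| 4 × 10 | one-sided lower | 97.6% | 92.2% | 83.0% | 77.2% |

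The 14-subject row shows that combining cohorts does not cure the problem. For scale, take 28/40 localized at ρ = 0.3. The design effect is 1 + 9 × 0.3 = 3.7 and the effective n is 40/3.7 = 10.8. The interval widens from 0.53–0.83 to 0.36–0.93.

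**3. Size of the nominal 5% exact McNemar test, 6 subjects.** Each site is discordant with probability d. Given discordance, the chance that it is IV-only is drawn once per subject from Beta(a, a), with a = (1−ρ)/(2ρ), so the average is 1/2. The p-value is 2·P(Bin(n, 1/2) ≤ min(b, c)), capped at 1, where b and c are the two discordant counts and n = b + c.

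| Sites per subject | d | ρ = 0.1 | 0.3 | 0.5 |
|---|---|---|---|---|
| 5 | 20% | 1.6% | 2.5% | 3.5% |
| 5 | 40% | 3.6% | 6.5% | 9.6% |
| 10 | 10% | 1.7% | 2.7% | 3.8% |
| 10 | 20% | 3.8% | 7.0% | 10.5% |
| 10 | 40% | 6.2% | 13.4% | 20.1% |
| 20 | 40% | 11.6% | 25.5% | 35.1% |

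**4. Control case.** If only the overall rate varies between subjects (6 × 10, rate 0.7, ICC 0.3 or 0.5) and the routes are equivalent within each subject, the simulated size is 2–3%. Inflation therefore comes only from clustering of direction.

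**5. Subject as unit.** The smallest two-sided p of an exact sign-flip test is 2 × (1/2)^6 = 0.031 with 6 subjects and 2 × (1/2)^5 = 0.0625 with 5.

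**The case against.** The study is descriptive by its own statement. No alpha, power or decision rule attaches to Tables 6, 8 or 9, dose escalation depends on ADRs, and per-subject localization rates with exact intervals are already planned (Table 5). This stands and limits the severity. It does not remove the problem: SAP 4.2 states formal hypotheses, Table 9 prints a p-value, and an interval labelled 95% claims that coverage whatever the status of the study.

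The McNemar argument needs a particular null, in which individual subjects favour one route and these preferences cancel on average. Since every Cohort 3 subject is injected at the same SC location, a regional-versus-systemic contrast could equally be a shared route effect, which the test is meant to detect. That is fair, and it makes the interval argument the stronger of the two. Inflation is also absent when few sites are discordant (step 3), and 20 sites per subject exceeds the 15 cutaneous codes, although oral or non-cutaneous sites could add to them. The ICCs are assumptions throughout.

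Data Listing 18 already shows each lesion by subject, so per-subject proportions can be derived for Cohorts 1 and 2. It has no route column, so this does not extend to IV versus SC in Cohort 3.

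**Conclusion.** The concern holds and should be fixed. Followed as written, the plan can produce lesion-level intervals that are too narrow and an IV/SC p-value that is too small. How far depends on quantities the documents do not give. At a true rate of 0.7 with 4 subjects, two-sided coverage runs from about 94% (5 lesions each, ICC 0.1) to about 60% (10 lesions each, ICC 0.5). McNemar size with 6 subjects runs from below 5% when discordance is rare to about 20% with 10 sites each, 40% discordant and ICC 0.5. It reaches about 35% with 20 sites each. The missing correction is certain; the size of its effect is not.

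Independently of any ICC, the unit is not fixed: the test uses sites, the accompanying text counts subjects, and Table 9 counts lesions. Two programmers could build different tables. The primary ADR proportion and the per-subject localization intervals are unaffected.

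**What to change.** 1. Keep the IV/SC cross-tabulation as descriptive and drop the site-level McNemar p-value. If a test is wanted, use an exact sign-flip test on each Cohort 3 subject's IV-minus-SC proportion and state its minimum p from step 5. It gives subjects equal weight, is conservative (size at most 2.5% in simulation with 6 subjects) and cannot reach 0.05 with 5 subjects.
2. In Tables 6 and 8, report each subject's lesion proportion and the mean of these, and label the pooled interval as descriptive and not adjusted for clustering. Plain exact intervals remain right for per-subject endpoints.
3. Define site, lesion and region once, and use one unit in the SAP 4.2 text and Table 9. As a separate point, state which of the two post-SC scans forms the pair, and add a route column to Data Listing 18.

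Clustered intervals are a weaker option at this size. With 4 subjects, 10 lesions each and ICC 0.3, a t-interval on subject rates covers 91% at rate 0.7, with median width 0.69 after truncation to 0–1. At rate 0.9 it covers 83%, and 17% of samples show no between-subject variation. If one is chosen, specify a fallback for identical subject rates, such as the exact interval with n equal to the number of subjects.

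The cost is wording in SAP 4.2 and protocol 9.5.3, three table shells and one listing, with no new data. Dropping or replacing a test named in the protocol may not count as administrative under protocol 3.3, so a formal amendment may be needed.
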